### **Guidance for Other Medications**

The investigator or participant's physician/health care provider are permitted to make adjustments in other therapies throughout the trial if clinically warranted. Guidance for specific medications which are permitted during the study is provided below.

1. Non-steroidal anti-inflammatory drugs (NSAIDs): NSAIDs may be used for minor ailments (e.g. minor injuries, osteoarthritis, upper respiratory tract infections) without prior consultation with the Sponsor Clinical Director. **Note:** Acetaminophen is a known hepatotoxin and is therefore prohibited.
2. HMG-CoA reductase inhibitors (statins) and ezetimibe: Concomitant use of a statin (e.g. atorvastatin, simvastatin) and/or ezetimibe is permitted if the regimen (agents and doses) has been stable for  $\geq 3$  months prior to screening. It is preferable that the lipid-lowering

[figure not shown]
regimen (agents and doses) remain stable throughout study participation (from screening through the post-study follow-up visit).

3. Antihypertensive medications:  $\leq 2$  anti-hypertensive agents are permitted. These may not include verapamil given potential for verapamil to perpetrate a DDI with K-757. It is preferable that doses of anti-hypertensive medications remain stable from randomization through the post-study follow-up visit.
4. Post-menopausal hormonal replacement therapy (HRT): Post-menopausal HRT is permissible, but participants should be on a stable HRT regimen at screening and are expected to remain on this stable regimen throughout study participation.
5. Thyroid Hormone Replacement Therapy: Thyroid hormone replacement medication (e.g., thyroxine) is permitted, but subjects should be on a stable dose for at least 3 months prior to screening. It is preferable that doses of thyroid hormone replacement remain stable throughout study participation (from screening through the post-study follow-up visit).
6. Nicotine/Nicotine products: Smoking is permitted during the study; however, participants should refrain from smoking  $>10$  cigarettes per week. No other forms of nicotine (other forms of tobacco, nicotine patch, e-cigarettes, vapes) are permitted during study participation. **Note**: Participants should avoid cigarette use at least 30 minutes prior to measuring blood pressure.
7. Ondansetron may be used as necessary to manage GI intolerance (see Section 7.1.1).
8. Anti-depressants: Anti-depressant agents that are not prohibited (see above) are permissible if the treatment regimen (agents and doses) has been stable for  $\geq 6$  months prior to screening. Permissible classes/agents include selective serotonin reuptake inhibitors (SSRIs; e.g. fluoxetine, sertraline), serotonin-norepinephrine reuptake inhibitors (e.g. desvenlafaxine, duloxetine), serotonin modulators (e.g. nefazadone, trazadone), and bupropion. It is preferable that anti-depressant regimens (agents and doses) remain stable throughout study participation (from screening through the post-study follow-up visit).
9. Supplements and/or Traditional Medicines: The use of herbal supplements and other natural products is allowed provided doses have been stable for at least 90 days prior to the screening visit. Increases in dose/frequency during the study are prohibited. Use of all such agents should be captured on the prior/concomitant medication CRFs.

### **Drug-drug interaction considerations**

No formal drug-drug interaction studies in humans have been conducted with K-757 or K-833.

Contact the Sponsor if there any questions about potential drug interactions with concomitant medications.

## 11. STUDY RESTRICTIONS AND REQUIREMENTS

### 11.1. Dietary and Physical Activity Requirements and Restrictions

#### Fasting Prior to Study Visits

1. Participants must attend visits V2, V6, V9, V12, and V13 in the fasted state. These visits should be scheduled in the morning.
2. Fasting is defined as at least 8 hours before the visit without food or liquids, except for water.
3. At fasted visits, the morning doses of study medication should be withheld until blood samples have been obtained (except V12 and V13 where there is no dosing).

#### Diet and Physical Activity Counseling

All participants will receive nutritional and physical activity counseling according to the SOA (Table 2). This counseling will be provided by a dietician or similar qualified healthcare professional.

Nutritional counseling will focus on calorie-reduction with an energy deficit of approximately 500 kcal/day based on the total energy expenditure (TEE) estimated once based on the weight at V2. Physical activity will also be encouraged (minimum 150 min of physical activity per week, e.g. walking or use of the stairs). **Note:** To minimize potential for variability in counseling between study sites, diet and activity counseling must be limited to that specified for the study and occur only at the site visits specified in Table 2. No diet or activity counseling may occur at other site visits or outside of site visits (e.g. by phone, text, email).

If a BMI  $\leq 22.5$  kg/m^2 is reached, the recommended energy intake should be recalculated with no kcal deficit (maintenance diet) for the remainder of the trial. As necessary, the investigator may consult with the Kallyope Clinical Director to discuss when a maintenance diet should be initiated.

#### Calculation of Estimated TEE

The TEE is calculated by multiplying the estimated Basal Metabolic Rate (BMR) (Table 10) with a Physical Activity Level value of 1.3.

**Table 10: Equation for Estimated BMR**

Sex	Age (years)	BMR (kcal/day)
Men	18 to 30	15.057 x weight at randomization in kg + 692.2
	31 to 60	11.472 x weight at randomization in kg + 873.1
	>60	11.711 x weight at randomization in kg + 587.7
Women	18 to 30	14.818 x weight at randomization in kg + 486.6
	31 to 60	8.126 x weight at randomization in kg + 845.6
	>60	9.082 x weight at randomization in kg + 658.5

**11.1.1. Alcohol Restrictions**

Participants are permitted to consume alcohol, as long as the amount is lower than 14 drinks/week for men and >7 drinks/week for women, where 1 drink= 5 ounces (150 mL) of wine or 12 ounces (360 mL) of beer or 1.5 ounces (45 mL) of hard liquor.

**11.1.2. Caffeine Restrictions**

Participants should avoid caffeine at least 30 minutes prior to measuring blood pressure.

**11.1.3. Smoking Restrictions**

Smoking is permitted during the study; however, participants will refrain from smoking >10 cigarettes per week. In addition, no other forms of nicotine (e.g. other forms of tobacco, nicotine patch, e-cigarettes, vapes) are permitted during the study.

Participants should avoid cigarette use at least 30 minutes prior to measuring blood pressure.

**11.1.4. Activity Restrictions**

See activity counseling above (Section 11.1).

**11.2. Contraceptive Requirements**Male study participants:

Must not donate sperm from the first dose of study drug until 14 days after the last dose of study drug.

If the partner is a non-pregnant female of child-bearing potential, they must use an appropriate method of contraception, which must include a condom with spermicidal cream or jelly, from the first dose of study drug until 14 days after the last dose of study drug which is more than 5 times the estimated half-life of K-757 and K-833. A male subject who has had a vasectomy must use a condom but is not required to use spermicidal jelly.

If a partner is pregnant, they must use a condom.

Note: Contraception/condom requirements are waived if partner is NOT of child-bearing potential (i.e. is male or is a female who is post-menopausal or surgically sterile [post-hysterectomy, post-bilateral oophorectomy, and/or post-bilateral salpingectomy]).

Female study participants of reproductive potential

Must agree to not donate eggs from the first dose of study drug until 14 days after the last dose of study drug.

Must agree to not donate eggs from the first dose of study drug until 14 days after the last dose of study drug.

Must either agree to remain abstinent from heterosexual activitya or use (or have their partner use) a birth control method that is highly effective and has low user dependency. Acceptable methods of birth control are:

- Progestogen-only implant (e.g. etonogestrel implant)
- Intrauterine device (IUD)
- Intrauterine hormone-releasing system (IUS)
- Bilateral tubal occlusion
- Vasectomized partner

a Abstinance can be used as the sole method of contraception if it is in line with the subject's preferred and usual lifestyle and if considered acceptable by local regulatory agencies and ethics committees. Periodic abstinance (e.g., calendar, ovulation, sympto-thermal, post-ovulation methods, etc.) and withdrawal are not acceptable methods of contraception.

The criteria specified in Section 8.1, Inclusion Criterion #8 must be met for a female subject to be considered not of reproductive potential for the purpose of this study.

## **12. RANDOMIZATION AND BLINDING**

### **12.1. Randomization and Blinding**

#### **12.1.1. Randomization Code Creation and Storage**

Randomization personnel of the Sponsor or designee will generate the randomization schedule. All randomization information will be stored in a secured area, accessible only by authorized personnel.

#### **12.1.2. Clinical Study Drug Blinding**

This is a double-blind study where the Sponsor, site staff and participants will be blinded to the treatment assignment.

#### **12.1.3. Clinical Trial Blind Maintenance/Unblinding Procedure (Blinded Studies Only)**

The study drug blind shall not be broken by the investigator unless information concerning the study drug is necessary for the medical treatment of the subject. If possible, the Sponsor medical monitor should be contacted before the blind is broken, unless doing so poses a risk to subject safety. The need for investigator unblinding should be discussed with the Sponsor first unless the unblinding needs to occur urgently to ensure subject safety.

Unblinding will be performed per the standard operating procedures of the study site. Any intentional or unintentional unblinding will be documented in the unblinding log and Clinical Study Report (CSR).

### 13. STUDY DRUG MATERIALS AND MANAGEMENT

#### 13.1. Study Drug

In this protocol, the term study medication refers to all or any of the drugs defined below and in Table 11 and Table 12.

Details regarding the dosage form description and strengths of the active drug and placebo can be found in the Pharmacy Manual or equivalent manual. Study drug will be packaged to support enrollment and replacement of participants as required.

The study site will be supplied to the study site / Investigator by the Sponsor with the following medication in a double-blind manner:

- K-757 30-mg and 60-mg capsules and placebo capsules. Capsules will be provided in polyvinyl chloride (PVC)/polyvinylidene chloride (PvDC) blisters with aluminum base as a primary package. Blister strips are then secondary packaged into wallet cards to meet the required dosing regimen. Participants are blinded as to the study treatment they receive.
- K-833 100-mg capsules and placebo capsules. Capsules will be provided in PVC/PvDC blisters with aluminum base as a primary package. Blister strips are then secondary packaged into wallet cards to meet the required dosing regimen. Participants are blinded as to the study treatment they receive.

Blister packs will be labeled with a single-panel label that will contain, but will not be limited to, the following: Sponsor's name and address, protocol number, packaging job/lot number, caution statement and storage conditions.

**Table 11: K-757 Investigational Product**

	Investigational Product
Product Name:	K-757
Dosage Form:	██████████
Unit Dose	Capsules: placebo, 30-mg and 60-mg potencies
Route of Administration	Oral
Physical Description	30 mg or 60 mg of K-757 and placebo ██████████ primary packaged in PVC/PvDC blisters with aluminum base and secondary packaged into wallet cards based on dosing regimen.
Manufacturer	██████████
Packaging / Distribution	██████████

Additional reference information and administration instructions can be found in the Pharmacy Manual.

**Table 12: K-833 Investigational Product**

	Investigational Product
Product Name:	K-833
Dosage Form:	██████████
Unit Dose	Capsules: placebo, 100-mg potencies
Route of Administration	Oral
Physical Description	100 mg of K-833 and placebo ██████████ ██████████ primary packaged in PVC/PvDC blisters with aluminum base and secondary packaged into wallet cards based on dosing regimen.
Manufacturer	██████████
Packaging / Distribution	██████████

### 13.2. Study Drug Packaging and Labeling

A clinical label will be affixed to study drug containers in accordance with local regulatory requirements.

### 13.3. Study Drug Storage

Study drug must be stored in a secure, limited-access location under the storage conditions specified on the label and must remain in the original container until dispensed. A daily temperature log of the drug storage area must be maintained.

K-757 and K-833 capsules should be stored in well-closed containers at room temperature (15 to 25 °C / 59 to 77 °F). The temperature excursion information can be found in the pharmacy manual or in the referenced compounding manual when applicable. Receipt and dispensing of study drug must be recorded by authorized personnel at the study site.

### 13.4. Administration

Participants will be blinded to treatment assignment and dose level at all times.

Study medication may be taken without regard to food.

#### 13.4.1. Dose Timing

The morning dose should be taken between 6 and 10AM.

The evening dose should be taken approximately 10 hours after the morning dose.

There should always be at least 6 hours in between doses.

#### 13.4.2. Missed Doses

If a subject did not take their scheduled dose:

1. If a morning dose is not taken by 12 noon, it should not be taken.

2. If an evening dose is not taken by 12 midnight, it should not be taken.
3. If a dose is missed, that dose should not be taken at a later time. It should be left in the blister pack and returned to the study site at the next site visit.

#### **13.4.3. Dosing Interruptions**

If multiple days of dosing are missed due to subject error, the participant may resume QD dosing for 3 days under PI discretion before returning to the BID regimen. If less than 2 days (4 consecutive doses) are missed, the subjects should resume the BID regimen.

If study medication is missed for  $\geq 7$  consecutive days, for any reason, the decision to resume should be based on discussion between the PI and Sponsor Clinical Director.

All dosing interruptions should be documented in the case report forms.

#### **13.5. Study Drug Accountability**

The Investigator is responsible for keeping accurate records of the study drug received from the Sponsor or designee, the amount dispensed to and returned by the participants, and the amount remaining at the end of the study. For all study sites, the local country sponsor personnel or designee will provide appropriate documentation that must be completed for study drug accountability, return, and destruction.

All ancillary supplies will be provided by either the study site or the Sponsor or designee, depending upon availability. The list of ancillary supplies and source information can be found in the Pharmacy Manual or in the referenced compounding manual when applicable. If provided by the Sponsor, unused ancillary supplies will be accounted for and disposed of as directed by the Sponsor or designee.

#### **13.6. Study Drug Handling and Disposal**

For all study sites, the local country sponsor personnel or designee will provide appropriate documentation that must be completed for study drug accountability, return, and destruction.

#### **13.7. Treatment Compliance**

Treatment compliance will be monitored throughout the duration of the study. Study medication will be reconciled at each visit, when new treatment wallets are administered to participants. A system to support subject adherence to BID dosing will be used at participating sites during the study. Dosing reminder texts and capture of anonymized subject AM/PM dosing will be done via a smart phone application and monitored centrally. No data from the application-based tool will be collected during the study. Actual dosing compliance is to be confirmed between the site staff and subjects at each study visit and upon return of the subject IMP blister cards. Missed doses will be quantified within the eCRF and tracked within the site drug accountability logs.

## 14. EFFICACY ASSESSMENTS

### 14.1. Body Measurements

Body weight should be measured at all site visits where indicated in the SOA, in the fasted state.

The scale should be calibrated prior to study start. A recalibration is not needed if calibration occurred within 3 months prior to the study start.

Body weight will be measured, in kilograms (kg) or pounds (lbs), using a standardized, digital scale. The scale must provide body weight in kg or lbs (unit conversion from pounds to kilograms by site staff is not permitted). The weighing process is as follows:

- The same scale should be used for each patient at all study visits where weight is measured.
- Weight will be taken in duplicate throughout the trial at approximately the same time of day, after voiding (i.e., forced void) and while wearing only a gown and underwear (no street clothes or shoes; socks do not need to be removed).
- Participants should be instructed to step gently onto the scale, place both feet together in the center of the scale and stand straight with eyes directed ahead. Participants should be instructed to stand still and not sway. Measurement will be recorded after the weight has stabilized.
- Body weight should be reported with precision to one decimal place (i.e., 0.1 kg or lbs). The 2 measurements should be recorded in the source documents. If the 2 measurements differ by more than 0.2 kg or lbs, a second set of duplicate measurements must be obtained as follows: (1) check the subject to ensure proper positioning as indicated above and (2) re-measure weight in duplicate. This process should be repeated, as needed until duplicate measurements that agree within 0.2 kg or lbs are obtained. This set of measurements should be recorded in the source documents and in the clinical database.

Height is measured without shoes in centimeters (one decimal). BMI will be calculated from screening data and must agree with inclusion criterion no. 4. Height will be measured at Screening only and will not need to be reassessed at subsequent visits where weight is required per the SOA. Body mass index equals a subject's weight in kilograms divided by the square of the height in meters (body mass index= $\text{kg}/\text{m}^2$ ). Body mass index will be rounded to the nearest whole number according to the standard convention of 0.1 to 0.4, round down, and 0.5 to 0.9, round up.

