### 1.1. Summary of Changes

Reason for Change	Section
Added optional genetic blood sample collection	Table 2, Section 14.3.2
Clarified the BMI upper range as 40.0 at screening in Inclusion Criterion #4	Synopsis, Section 8.1
Clarified contraception requirements in Inclusion Criterion #8	Synopsis, Section 8.1, Section 11.2
Clarified obesity exclusion medication use in Exclusion Criterion #5	Synopsis, Section 8.2
Clarified when a participant may be enrolled who has uncontrolled thyroid disease in Exclusion Criterion #10	Synopsis, Section 8.2
Clarified prohibited medications in Exclusion Criterion #17	Synopsis, Section 8.2
Clarified Exclusion Criterion #18 regarding various diseases and reasons for exclusion	Synopsis, Section 8.2
Updated Exclusion Criterion #33 to be consistent with Section 14.2: Blood pressure should be taken seated not semi-recumbent and after resting 5 minutes	Synopsis, Section 8.2
Added clarification to Exclusion Criterion #36 regarding the use of benzodiazepines	Synopsis, Section 8.2
Added hemoglobin and hemoglobinopathy to Exclusion Criterion #41	Synopsis, Section 8.2
Added clarification to Exclusion Criterion #44 pertaining to interpretation of efficacy and/or safety results	Synopsis, Section 8.2
Added Exclusion Criterion #47 regarding use of opiate medications	Synopsis, Section 8.2
Added Exclusion Criterion #48 regarding use of medications that affect body weight	Synopsis, Section 8.2

Administrative	
Clarified which exclusion criteria need to be confirmed prior to randomization Fixed Day 57/Week 8 column heading error on 2 nd page of Table 2	Table 2
Added stimulant and opiate medications to the Prohibited Medications list	Section 10.1
Clarified diet and activity counseling will be limited to the protocol guidelines	Section 11.1
Clarified dosing interruptions procedures due to subject error	Section 13.4.3

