## 5.5. Rationale for Study Population

The trial population will consist of individuals who are obese (BMI 30.0 to 40.0 kg/m^2, inclusive) These participants represent a clinically relevant population for pharmacotherapeutic weight management as they are at significant risk for weight related morbidities (such as hypertension, dyslipidemia, obstructive sleep apnea) and mortality and are likely to benefit from weight reduction. People with known cardiovascular disease (CVD) are excluded given the early stage of development and limited characterization of the safety profiles of the study regimens. A BMI > 40.0kg/m^2 is exclusionary to limit potential for occult CVD or other health issues that might increase the risk of participating in an early-stage clinical trial. People with T2DM are excluded due to the well-described confounding effect that improved glycemic control has on response to weight-loss interventions.

As first line treatment in weight management is lifestyle modification through a reduced-calorie diet and increased physical activity, only people who have tried but failed to attain weight loss goals with lifestyle modification will be eligible for participation.

Sex is an important response covariate with females typically achieving greater weight loss than males in obesity trials. Randomization will be stratified by sex to minimize potential bias. Weight loss trials have historically enrolled substantially more female than male participants. To ensure meaningful representation of both sexes, neither strata will be permitted to exceed 70% of total enrollment. Females of childbearing potential (FOCBP) are eligible for participation. Given the early stage of development and current lack of definitive embryo-fetal toxicology data for either K-757 or K-833, FOCBP must be using highly effective contraception with low user-dependence and undergo pregnancy testing at screening and specified timepoints during study participation.

Given the priority of avoiding spurious liver toxicity signals, excessive alcohol consumption, known history of liver disease (other than non-alcoholic fatty liver disease [NAFLD]), and excessive elevations in ALT, AST, and/or bilirubin at screening are exclusionary as specified in Section 8.2.

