## 8. SELECTION AND WITHDRAWAL OF PARTICIPANTS

### 8.1. Subject Inclusion Criteria

All entry criteria, including laboratory test results, need to be confirmed before administration of the first dose of study drug.

In order to be eligible for participation in this trial, the subject must:

1. Understand the trial procedures and agree to participate by providing written informed consent prior to trial related activities. Trial-related activities are any procedures that are carried out as part of the trial, including activities to determine suitability for the trial.
2. Be willing and able to comply with all trial procedures and restrictions, including following study diet requirements.
3. Be a male or female, age 18 to 70 years of age, inclusive, at the time of signing informed consent.
4. Have a body mass index (BMI) of 30.0 to 40.0. kg/m^2, inclusive at screening.
5. History of at least one self-reported unsuccessful dietary effort to lose body weight.
6. Be weight stable (<5% variation) over the last 3 months (by subject report).
7. Be a nonsmoker or has smoked  $\leq 10$  cigarettes per week for at least 3 months and agrees not to exceed this for the duration of study participation; has not used other nicotine containing products (e.g. other forms of tobacco, nicotine patch, e-cigarettes, vapes) for at least 3 months and agrees to abstain from such products throughout study participation.
8. Meet the following birth control requirements:
  - a. Is a male subject who agrees to **all** of the following:
    - If partner is a non-pregnant female of child-bearing potential: To use an appropriate method of contraception, which must include a condom with spermicidal cream or jelly, from the first dose of study drug until 14 days after the last dose of study drug. A male subject who has had a vasectomy procedure must use a condom, but is not required to use spermicidal cream or jelly.
    - If partner is pregnant, to use a condom
    - Note: Contraception/condom requirements are waived if partner is NOT of child-bearing potential (i.e. is male or is a female who is post-menopausal or surgically sterile [post-hysterectomy, post-bilateral oophorectomy, and/or post-bilateral salpingectomy]).
    - To not donate sperm from the first dose of study drug until 14 days after the last dose of study drug.

OR

- b. Is a female who is of non-childbearing potential defined by at least 1 of the following criteria:

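### Protocol 14.1 rounds BMI to a whole number beside the requirement to meet a one-decimal eligibility range (30.0 to 40.0), without limiting the rounding to display

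*Protocol*

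**What the plan says.** Criterion 4, in the Synopsis and in Protocol 8.1, reads "Have a body mass index (BMI) of 30.0 to 40.0" kg/m², inclusive, at screening. Protocol 5.5 repeats the range and adds that a BMI above 40.0 "is exclusionary to limit potential for occult CVD or other health issues that might increase the risk of participating" in an early-stage trial.

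Protocol 14.1 says how BMI is obtained. Weight and height are each recorded to one decimal (for weight: "Body weight should be reported with precision to one decimal place"). It links BMI to eligibility: "BMI will be calculated from screening data and must agree with inclusion criterion no. 4". After the formula, the same paragraph adds "Body mass index will be rounded to the nearest whole number according to the standard convention of 0.1 to 0.4, round down", with 0.5 to 0.9 rounded up.

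The SAP does not settle the matter. SAP 5.4 gives the BMI formula without a rounding step, but uses it only when BMI is not already available. SAP 5.1.1 covers decimal places in summary tables only. SAP 5.8.3 splits a subgroup at BMI 35.

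**The concern.** The rounding removes the decimal in which criterion 4 is written. The only use of BMI that 14.1 names is the eligibility check, so a coordinator following that section in order could reasonably round first and then compare with 30 to 40. Another site could compare the unrounded value. Both could say they followed the protocol.

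Three consequences follow for borderline screenees:

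- **Enrolment.** A BMI of 29.6 or 40.3 would be accepted at one site and refused at another. The decision is hard to reverse: Protocol 8.2 does not allow rescreening unless specified, and criterion 39 excludes anyone who has already signed consent for this trial.
- **Deviations.** SAP 5.3 has the sponsor classify protocol deviations. Enrolling someone at 40.3 is a deviation on one reading and compliant on the other.
- **Subgroup.** If a rounded BMI is recorded, SAP 5.4 would use it, and SAP 5.8.3 would then place some participants on the wrong side of 35. The documents do not say that a rounded value is recorded, so this is conditional.

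**Working it through.** The plan gives no figure to reproduce here. The check applies the stated rule to values near each limit.

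**Inputs.** Range 30.0 to 40.0 inclusive (Protocol 8.1); rounding to a whole number with 0.5 and above going up (Protocol 14.1); weight to 0.1 kg and height to 0.1 cm (Protocol 14.1); subgroup cut at 35 (SAP 5.8.3). Heights of 1.50 to 1.90 m are assumed, because the documents give no height distribution.

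**Step 1: decisions under the two readings.**

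| BMI | Whole number | Rounded value in 30–40? | One-decimal value in 30.0–40.0? |
|---|---|---|---|
| 29.4 | 29 | no | no |
| 29.5 | 30 | yes | no |
| 29.9 | 30 | yes | no |
| 30.0 | 30 | yes | yes |
| 40.0 | 40 | yes | yes |
| 40.1 | 40 | yes | no |
| 40.4 | 40 | yes | no |
| 40.5 | 41 | no | no |

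The discordant one-decimal values are 29.5, 29.6, 29.7, 29.8, 29.9, 40.1, 40.2, 40.3 and 40.4: nine in all. On unrounded BMI the admitted range becomes 29.5 to <40.5. Its width is 40.5 − 29.5 = 11 units against 40 − 30 = 10, or 10% wider.

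This assumes one rounding step. If BMI is first rounded to one decimal and then to a whole number, the range is 29.45 to <40.45, a shift of 0.05.

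**Step 2: the same shift in kilograms.** Weight = BMI × height². At 1.70 m, height² = 2.89 m²:

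- Lower limit: 30.0 × 2.89 = 86.7 kg; 29.5 × 2.89 = 85.3 kg.
- Upper limit: 40.0 × 2.89 = 115.6 kg; 40.5 × 2.89 = 117.0 kg.

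The shift is 0.5 × height²: 1.1 kg at 1.50 m, 1.4 kg at 1.70 m and 1.8 kg at 1.90 m.

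**Step 3: comparison with recording precision.** The largest BMI error from recording is approximately BMI × (0.05/weight + 2 × 0.05/height in cm).

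- 1.50 m, BMI 40 (90 kg): 40 × (0.05/90 + 0.1/150) = 0.049.
- 1.90 m, BMI 30 (108.3 kg): 30 × (0.05/108.3 + 0.1/190) = 0.030.

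The rounding can therefore move BMI by 0.5/0.049 ≈ 10 to 0.5/0.030 ≈ 17 times as much as the recording precision.

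**Step 4: subgroup cut.** A BMI from 34.5 to <35 rounds to 35 and would move into the ≥35 group if the rounded value were used.

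**The case against.** The strongest reply is that criterion 4 plainly governs. Section 14.1 tells sites that BMI must agree with the criterion, which puts the criterion first. The rounding sentence comes later and does not mention eligibility. Its convention is written in tenths, so it presupposes a one-decimal BMI that could be checked before rounding. The summary of changes records "Clarified the BMI upper range as 40.0 at screening in Inclusion Criterion #4". Protocol 11.1 uses another one-decimal threshold: when a BMI of 22.5 or less "is reached, the recommended energy intake should be recalculated with no kcal deficit", and a whole-number BMI can never equal 22.5.

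Most of this stands, and it makes criterion 4 the more natural reading. It does not supply the missing instruction: agreement with criterion 4 could be tested before or after rounding, and no text says which. The 22.5 threshold shows only the precision intended. Reaching it from 30.0 would need a loss of 1 − 22.5/30 = 25%, so it has little practical role.

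It can also be said that the effect is trivial and that recording precision is too narrow a yardstick. Section 14.1 itself accepts duplicate weights 0.2 kg apart, which is 0.2/2.89 = 0.07 kg/m² at 1.70 m. The ratio in step 3 should therefore be read only as showing that the rounding discards detail that sites are required to collect, not as a measure of harm. The small size is accepted; the ambiguity remains.

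**Conclusion.** The concern holds: the protocol carries two incompatible precisions for one eligibility threshold and does not say which applies. The effect is confined to screenees within 0.5 kg/m² of either limit, and it arises only at sites that apply the rounding to eligibility.

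The documents give no BMI distribution, so the number affected cannot be estimated; each 1% of participants in the two bands would be 0.01 × 150 = 1.5 people.

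BMI is not in the primary model (SAP 5.8.1.2) and is not a stratification factor (Protocol 7.3.1). Eligibility is decided before blinded randomization, so no effect on power or on bias between arms is expected. The point deserves correction because it concerns an eligibility rule whose upper limit Protocol 5.5 justifies by participant risk, and because the correction is nearly free.

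**What to change.** Reconcile Protocol 14.1 with criterion 4 and Protocol 5.5. Either delete the whole-number rounding or state that it is for display only, and say at what precision BMI is compared with criterion 4. The choice should be explicit: unrounded BMI gives 30 to 40 exactly, whereas rounding first to one decimal gives 29.95 to <40.05.

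As a safeguard, add one sentence covering SAP 5.4 and 5.8.3: baseline BMI is derived from recorded weight and height and used unrounded for the <35 / ≥35 subgroup.

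The cost is one sentence in each document, with no new data or visits. At any site that has been applying the rounded value, a few borderline screenees could be decided differently.
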